6.5 Randomization and Allocation Procedures

Each eligible subject (ie, meets inclusion criteria, and does not fulfill any exclusion criteria) will be randomly assigned to 1 of the 2 groups via an IRT, according to a 2:1 ratio (2 subjects included in the CYD Dengue Vaccine Group for 1 subject included in the control Group). Site staff will connect to the IRT, enter identification and security information, and confirm a minimal amount of data in response to IRT prompts. The IRT will then state the vaccine assignment (code number). Subject numbers will be recorded in the CRB and will not be reassigned for any reason. The full detailed procedures for randomization are described in the Operating Guidelines.

Subject numbers that are assigned by the IRT system will consist of a 12-digit string (a 3-digit country code, a 4 digit study center identifier, and a 5-digit subject identifier connected by “-”). For example, Subject 0760001-00001 is the first subject enrolled in center number 1 in Brazil (076 being Brazil country code). Subject numbers should not be reassigned for any reason. The randomization codes will be kept securely in the IRT.

Randomization will be performed with permuted block method with stratification by site.

A double randomization system will be used, this implies that the subject treatment allocation will be separated from doses dispensing. Each dose will have both a code number and a dose number. The code number will be used by the IRT while the dose number will be entered in the CRB. The unique dose numbers will be defined according to a random list to ensure that dose numbers cannot be used to distinguish between treatment groups.

The R&D Site Quality Operations Department at Sanofi Pasteur will hold the randomization codes in a secured location.

Notes:

- Subjects who previously tested negative by RDT for previous exposure to dengue can be re-screened using IgG ELISA. Subjects who are re-screened will be allocated a new subject number.
- If a subject is eligible but not randomized during the ESDR hold, the subject will be asked to come back to the site after the hold. The subject will then be re-screened and randomized.

However, the subject will not be re-tested for previous exposure to dengue by RDT or IgG ELISA. The subject will be allocated a new subject number.

6.6 Treatment Compliance

The following measures will ensure that the vaccine doses administered comply with those planned, and that any non-compliance is documented so that it can be accounted for in the data analyses:

- All vaccinations will be administered by qualified study personnel
- The person in charge of product management at the site will maintain accountability records of product delivery to the study site, product inventory at the site, dose(s) given to each subject, and the disposal of unused or wasted doses

6.7 Concomitant Medications and Other Therapies

At the time of enrollment, ongoing medications and other therapies (eg, blood products) should be recorded in the source document as well as new medications prescribed for new medical conditions / AEs during study participation.

Documentation in the CRB of ongoing concomitant medication(s) will be limited to specific categories of medication(s) of interest beginning on the day of vaccination. This may include medications of interest that were started prior to the day of vaccination.

Reportable medications will be collected in the CRB from the day of each vaccination to the end of the solicited and unsolicited follow-up period (eg, 28-day safety follow-up) as they may impact the response to the vaccination and impact the consistency of the information collected on concomitant medications at any vaccination.

Reportable medications include medications that impact or may impact the consistency of the safety information collected after any vaccination and/or the immune response to vaccination. Three standard categories of reportable medications are defined:

- Category 1: medications impacting or that may have an impact on the evaluation of the safety (eg, antipyretics, analgesics, and non-steroidal anti-inflammatory drugs [NSAIDs], steroids/corticosteroids). *Note: inhaled and topical steroids should not be captured.*
- Category 2: medications impacting or that may have an impact on the immune response.
 - Immunosuppressive therapy such as anti-cancer chemotherapy or radiation therapy or long-term systemic corticosteroids (for more than 2 consecutive weeks) in the 4 weeks after study injection
 - Immune globulins, blood or blood-derived products in the 3 months before the first study injection, in the 4 weeks before second and third injection, and in the 4 weeks after any injection
 - Any vaccine (other than the study vaccine) in the 4 weeks before second and third injection, and in the 4 weeks after any injection
- Category 3: medications impacting or that may have an impact on both the safety and the immune response (eg, steroids/corticosteroids)

The information reported in the CRB for each reported medication will be limited to:

- Trade name.
- Origin of prescription: prophylaxis Yes/No. Medication(s) prescribed for AE prophylaxis will be recorded in the Action Taken of the AE collection tables.
- Medication category (1, 2, or 3).
- Start and stop dates.

Dosage and administration route, homeopathic medication, topical, and inhaled steroids, as well as topical, ophthalmic, and ear treatments will not be recorded. Topical analgesics should not be applied at the site of vaccination; however, if they are applied inadvertently to the vaccination site, they should be recorded as a Category 1 medication in this specific instance.

Medications given in response to an AE will be captured in the “Action Taken” section of the AE CRF only. No details will be recorded in the concomitant medication CRF unless the medication(s) received belongs to one of the pre-listed categories. Medications will not be coded.

7 Management of Samples

Blood samples for the assessment of:

- Screening characteristics will be collected at Screening Visit (if results not already available from routine periodical tests)
- Dengue, YF, and Zika baseline status will be collected at Visit 1
- Dengue neutralizing Abs, CD4 count, and HIV viral load will be collected at Visits 4, 6, and 8
- Dengue vaccinal viremia will be collected at Visits 2 and 3

See the [Table of Study Procedures](#) and [Section 5.1](#) for details of the sampling schedule.

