Likewise, the safety of vaccines against JE has been assessed in a very limited number of HIV-positive subjects, all of whom were children. In 2 independent studies involving HIV-positive Thai children, no severe AEs were reported (40) (41).

It was observed that the stimulation of the immune system with vaccination may transiently increase HIV viremia, through heterologous transactivation. This usually resolves within 4 weeks (42) (43). However, this increase does not have clinical implications, as it does not correspond to virologic failure and it is not related to ART resistance. Hence, there is a possibility that vaccination against dengue is associated with this phenomenon in some subjects (42). However, in patients who received a live-attenuated oral cholera vaccine, no such activation was observed and there were no significant changes in CD4 count and HIV-1 viral load between vaccine and placebo groups (44). As per Brazil National Recommendations on vaccination of HIV-positive population, CD4 cells count will be checked before each injection (43).

Thus, and based on the scarce data on the vaccination of HIV-positive subjects against other FV (YF and JE), no safety signals are expected to occur in this descriptive study.

Placebo

No ARs are expected from placebo, except local reactions due to the injection process (eg, bruising, local pain).

All subjects

Potential risks may also include the AEs of blood sampling (ie, the discomfort from having blood taken lasting only seconds to minutes) and/or bruising.

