It is important to note that, if the attempt(s) to collect blood is (are) unsuccessful, the subject should be given the opportunity for another attempt within the Visit window. If a blood sample cannot be obtained, the reason will be recorded in the blood sampling page of the CRF.

- 5) Remind the subject to call the study center if a serious medical event occurs.
- 6) Arrange an appointment for the next visit (V04; at V01 + 28D [+14 days]).
- 7) Complete the relevant CRF pages for this visit.

Visit 4 (Inj 1+28D [+14 days]): Collection of Safety Information and Blood Sample

- 1) Collect DC1 and check the information entered into it by interviewing the subject and request information concerning any medical event, serious, or not, that may have occurred since Visit 3
- 2) Record any AEs and any reportable concomitant medications
- 3) Perform a physical examination and record the subject's axillary temperature (if necessary)
- 4) Obtain a blood sample (see [Section 7.1](#) for detailed instructions regarding the handling of blood samples), record the date of collection

It is important to note that, if the attempt(s) to collect blood is (are) unsuccessful, the subject should be given the opportunity for another attempt within the Visit window. If a blood sample cannot be obtained, the reason will be recorded in the blood sampling page of the CRF.

- 5) Remind the subject to call the study center if a serious medical event occurs
- 6) Provide the subject with DC2 and remind her/him to bring it back when she/he returns for Visit 5
- 7) Arrange an appointment for the next visit (V05; at V01 + 6 months (M6) [\pm 20 days])
- 8) Complete the relevant CRF pages for this visit

Visit 5 (Inj 2 [M6; \pm 20 days]): Collection of safety information and vaccination

- 1) Collect DC2 and check the information entered into it by interviewing the subject and request information concerning any medical event, serious, or not, that may have occurred since last Visit

- 2) Record any reportable concomitant medications
- 3) Perform a physical examination and record the subject's axillary temperature before injection
- 4) Check any contraindication to vaccination
- 5) Check for confirmation of previous exposure to dengue (from PRNT laboratory results)
- 6) Perform a urine pregnancy test for all women enrolled in the study
- 7) The person in charge of injections ("vaccinator") or authorized designee contacts the IRT to obtain the assigned product to be administered

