5.2.5 Exclusion Criteria

Exclusion criteria will be checked at Screening Visit and again at the first vaccination visit (V01 at D0). An individual fulfilling *any* of the following criteria is to be excluded from study enrollment:

An individual fulfilling *any* of the following criteria is to be excluded from trial enrollment:

- 1) Subject is pregnant, or lactating, or of childbearing potential (to be considered of non-childbearing potential, a female must be pre-menarche or post-menopausal for at least 1 year,

surgically sterile, or using an effective method of contraception or abstinence from at least 4 weeks prior to the first vaccination until at least 4 weeks after the last vaccination).

- 2) Participation at the time of study enrollment (or in the 4 weeks preceding the first trial vaccination) or planned participation during the present trial period in another clinical trial investigating a vaccine, drug, medical device, or medical procedure.
- 3) Receipt of any vaccine in the 4 weeks preceding the first trial vaccination or planned receipt of any vaccine in the 4 weeks following any trial vaccination.
- 4) Previous vaccination against dengue disease with either the trial vaccine or another vaccine.
- 5) Receipt of immune globulins, blood or blood-derived products in the past 3 months.
- 6) Self-reported or suspected congenital or acquired immunodeficiency, except HIV; or receipt of immunosuppressive therapy such as anti-cancer chemotherapy or radiation therapy within the preceding 6 months; or long-term systemic corticosteroid therapy (prednisone or equivalent for more than 2 consecutive weeks within the past 3 months).
- 7) Previous AIDS, defined as the occurrence of opportunistic infection in the last 2 years before consent.
- 8) Known systemic hypersensitivity to any of the vaccine components, or history of a life-threatening reaction to the vaccines used in the trial or to a vaccine containing any of the same substances.
- 9) Deprived of freedom by an administrative or court order, or in an emergency setting, or hospitalized involuntarily.
- 10) Current alcohol abuse or drug addiction.
- 11) Chronic illness that, in the opinion of the Investigator, is at a stage where it might interfere with trial conduct or completion.

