7.1.1.1 Blood Sample for Screening Characteristics Assessment

Approximately 14 mL (according to local laboratories) of blood will be collected from potential subjects in order to perform laboratory tests, including assessment of previous exposure to dengue, HBsAg, HCV Ab, hematology (hemoglobin, hematocrit, platelet count, white blood cells

count), biochemistry (AST, ALT, urea, and creatinine)^a. For subjects for whom HIV viral load and CD4 count have not been assessed within 2 months before the Screening Visit, an additional volume of blood (10 mL per test) will be required before the Screening Visit to perform the tests. The screening analyses will be performed at local laboratories. For subjects for whom these tests have been performed in appropriate time windows (within 4 weeks before injection for hepatitis serology, hematology, and biochemistry; within 2 months for HIV viral load and CD4 count) as part of the subject's routine follow-up, no new tests will be required.

Also, subject' previous exposure to dengue will be assessed using a RDT (OnSite™ Dengue IgG/IgM3.0 Combo Rapid Test commercialized by CTK Biotech, Inc.) or ELISA (Anti-Dengue IgG ELISA commercialized by Euroimmun).

7.1.1.2 Blood Sample for Dengue, YF, and Zika Serostatus, Dengue Neutralizing Antibodies, CD4 Count, and HIV Viral Load Assessments

At V01 (before first vaccination injection) for all subjects, 9 mL of blood will be collected in order to assess dengue, YF, and Zika status, as well as baseline dengue neutralizing Ab levels (PRNT).

At V04, V06, and V08 for all subjects, 24 mL of blood will be collected in order to assess dengue neutralizing Ab levels, CD4 count, and HIV viral load, 28 days post-injection. See [Table 5.1](#) for blood samples volumes for each laboratory test.

In addition, for subjects for whom HIV viral load and CD4 count have not been assessed within 2 months before Inj 2 (Visit 5) or Inj 3 (Visit 7), an additional volume of blood (10 mL per test) will be required before injection visits to perform the tests and check the contraindication to further vaccination. The tests will be performed at local laboratories.

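### Protocol 6.7 ends CRB reporting of other vaccines and blood products 4 weeks after each injection, but the PRNT, CD4 and HIV-RNA samples may be drawn to day 42

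*Protocol*

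**What the plan says.** **Reporting windows (Protocol 6.7).** The Category 2 entry for vaccines reads "Any vaccine (other than the study vaccine) in the 4 weeks before second and third injection, and in the 4 weeks after any injection". Blood products are reportable as "Immune globulins, blood or blood-derived products in the 3 months before the first study injection", then for 4 weeks before injections 2 and 3 and for 4 weeks after any injection. The general rule is "Reportable medications will be collected in the CRB from the day of each vaccination to the end of the solicited and unsolicited follow-up period", with a 28-day follow-up given as an example.

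**Sample window (Protocol 5.1.4 and 7.1.1.2).** The first post-injection sampling visit is "Visit 4 (Inj 1+28D [+14 days]): Collection of Safety Information and Blood Sample". V06 and V08 carry the same +14 days. Section 7.1.1.2 says "At V04, V06, and V08 for all subjects, 24 mL of blood will be collected", and that blood serves PRNT, CD4 and HIV viral load.

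**Eligibility (Protocol 5.2.5).** Exclusion criterion 3 covers other vaccines planned within 4 weeks after a study injection. Criterion 5 excludes for "Receipt of immune globulins, blood or blood-derived products in the past 3 months".

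**Why exposure matters (Protocol 1.3.2, 5.5, 10.7).** Section 1.3.2 notes that "the stimulation of the immune system with vaccination may transiently increase HIV viremia", usually settling within 4 weeks. Under 5.5 and 10.7, HIV RNA above 1000 copies/mL after being undetectable, or a CD4 fall of more than 30%, is an SAE unless non-adherence or another cause explains it. A repeat test follows 4 weeks later.

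**The concern.** Section 6.7 collects these items because they may affect the response to vaccination, yet its window can close before that response is measured. The avoidance period and the reporting period end at the same point, so a routine vaccine that was put off is most naturally given just as it stops being reportable.

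Two decisions need this information. One is the judgement, for a single subject under blind, of whether anything other than the study product explains an HIV-RNA or CD4 signal. The other is the review of whether a late but in-window sample belongs in the per-protocol set (PPAS). Both can be made without the exposure being in the CRB.

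The blood-product look-back raises a related question. The protocol treats 3 months as the period of interference before injection 1 but asks about only 4 weeks before injections 2 and 3.

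**Working it through.** The plan's one stated design figure reproduces: 1 − 0.97^100 = 0.9524, against the 95% in Protocol 12.5. It has no bearing on this point.

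**1. Length of the gap.**
- Last permitted sample day: 28 + 14 = 42. Last reportable day: 28.
- Gap: 42 − 28 = 14 days, which is 14/42 = 33% of the longest injection-to-sample interval. Over three injections, at most 3 × 14 = 42 days.
- Confirmatory draw: 28 + 28 = day 56 to 42 + 28 = day 70, which is 28 to 42 days past the reporting limit.

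**2. Whether another provision captures a preventive vaccine on days 29 to 42.**
- Look-back before injection 2. Taking month 6 as day 182 (assumption) with ±20 days, it opens between 182 − 20 − 28 = day 134 and 182 + 20 − 28 = day 174. It does not reach back to days 29 to 42.
- Source documents (6.7) take new drugs prescribed for new conditions or AEs. A preventive vaccine is neither.
- The sampling visits (5.1.4) record reportable medications, so the 6.7 cut-off governs there too.
- DC2 and DC4 are handed out at V04 and V06 and collect medications tied to an event.
- The PPAS (Protocol 12.2.3, SAP 5.2.2) excludes prohibited medication by pointing to 6.7, which lists reportable items and names none as prohibited. The SAP's additional criterion needs a protocol violation, and a vaccine on day 29 is not one.

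**3. A compliant example.** Vaccine on day 29, sample on day 42: 42 − 29 = 13 days, inside the 4 weeks (28 days) in which Protocol 1.3.2 expects a transient rise. The repeat test falls on day 70, and 70 − 29 = 41 days, outside it.

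**4. Effect on group titers.** If a fraction f of a group is exposed and the exposure multiplies titers by k, the GMT is multiplied by k^f. The documents give neither f nor k, so all values are assumptions.

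| f | k = 4 | k = 0.5 |
|---|---|---|
| 1% | 1.014 | 0.993 |
| 2% | 1.028 | 0.986 |
| 5% | 1.072 | 0.966 |
| 10% | 1.149 | 0.933 |

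In expectation the same factor applies to the placebo group.

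**5. Blood products before injections 2 and 3.** The period used before injection 1 is 3 months (about 91 days); the reporting look-back later is 28 days. 91 − 28 = 63 days, about 2 of the 3 months, are not reportable. Blood products appear in neither contraindication list (5.2.7.1, 5.2.7.2), so receipt in those 63 days is neither reportable nor a bar to the injection.

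**The case against.** The strongest reply is that much of this is covered elsewhere.

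- **Source records.** Drugs and blood products given for a new condition reach the source documents throughout participation, and each sampling visit includes an interview. This stands for treatments. It does not stand for a preventive vaccine, which is why that is the clearest case.
- **Investigator judgement.** Whether another cause explains a signal is decided by the investigator during SAE reporting, with a duty under Protocol 10 to obtain the necessary documentation. It is not derived from the concomitant-medication data. This stands in part: an investigator may ask about vaccines, but nothing in the two documents requires it for days 29 to 42.
- **Unseen instructions.** The 28 days in the general rule is only an example, and detailed collection rules sit in CRF instructions outside these documents. However, the 4-week limits for vaccines and blood products are stated outright.

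A reader might also infer three stronger points that the documents do not support.

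- **That such exposures will be read as effects of the study product.** The signals require other causes to be ruled out, and a randomized, observer-blind placebo group has the same window. Exposure is therefore balanced in expectation, though not necessarily in 50 controls.
- **That the gap could trigger a study hold.** Holds count confirmed, otherwise unexplained cases. At full enrolment they need 0.10 × 150 = 15 subjects (CD4) or 0.20 × 150 = 30 (HIV RNA). A transient viremia rise would usually have gone by the repeat test.
- **That immunosuppressants share the look-back problem.** Section 5.2.7.2 already applies 6-month and 3-month look-backs to them at injections 2 and 3. For long-term corticosteroids the post-injection gap is empty: a course begun on day 29 has run only 14 days by day 42, and Category 2 requires more than 2 weeks.

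**Conclusion.** The mismatch is in the text and does not depend on any assumption: up to 14 days before each of three endpoint samples in which a new vaccine or blood product is not CRB-reportable. It affects only subjects sampled after day 28 who have a new exposure in that interval. The documents give neither share, so no count of affected samples can be supported.

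The consequence is limited. An individual's first CD4 or HIV-RNA signal may be assessed, or a PPAS decision made, without a relevant exposure on record. Group GMTs would shift by about 7% if 5% were exposed and titers rose 4-fold (both assumed), in placebo as well as vaccine subjects in expectation. The blood-product look-back is a separate inconsistency of about 2 of 3 months before injections 2 and 3. This is a low-cost improvement to data collection and not a threat to the trial's main conclusions.

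**What to change.** - In Protocol 6.7, end Category 2 and 3 CRB reporting at the date of the V04, V06 or V08 sample, and at the confirmatory CD4/HIV-RNA draw where one is taken. The gap before each sample then becomes 0 days.
- In 6.7, set the blood-product reporting look-back before injections 2 and 3 to the 3 months used before injection 1.
- In the SAE or Safety Complementary Information CRF for a CD4 or HIV-RNA signal, record any other vaccine since the injection, with its date.
- In 6.7 and the PPAS definition, state how such exposures are handled.

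The sponsor should reconcile the vaccine avoidance period and the contraindication lists with the sample window. No clinical rule is proposed here.

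The cost is wording in 6.7, the PPAS definition and the CRF instructions, plus one dated item, with no extra visit or sample. The downside is slightly longer recall at visits that already review concomitant therapy.

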7.1 Sample Collection

7.1.1 Blood Samples

All the following blood samples will be collected in tubes provided by or recommended by the Sponsor. Immediately prior to the blood draw, the staff member performing the procedure will verify the subject's identity; will write the assigned subject's number on the pre-printed label that contains that subject's number and the sampling stage; and will attach the label to the tube. When vaccination and blood sample collection occur at the same Visit and vaccine is given only in one of the arms, blood is to be taken from the limb opposite to the one that will be used for vaccination.

